Date: September 1, 2021

Title: Comparison Effects Of Blue Prescription Program, Home Exercise Program And Supervised Exercise Approaches On Type 2 Diabetic Women.

Identifiers: NCT05479435

STUDY PROTOCOL

Participants: Individuals diagnosed with Type 2 Diabetes were recruited from Balikesir Provincial Health Directorate, Edremit District Health Directorate Healthy Life Center. They were 60 people who were assigned to the groups by using a randomization program.

Inclusion Criteria:

Age between 25-65 years.

Diagnosis of Type 2 Diabetes for at least 5 years.

HbA1c value > 6.5% or fasting blood glucose > 126 mg/dL.

Ability to walk independently.

Voluntary participation in the research.

Exclusion Criteria:

Type 1 Diabetes Mellitus.

Use of insulin.

Orthopedic or neurological conditions hindering exercise.

Cardiovascular, pulmonary, or systemic diseases contraindicating exercise.

Recruitment Details: The study commenced on September 1, 2021, at Balikesir Provincial Health Directorate, Edremit District, Health Directorate's Healthy Life Center in Balikesir, Turkey.

Evaluated Parameters:

Glycosylated Hemoglobin Change: Hemoglobin A1c is a blood test used to measure the effectiveness of treatment in diabetes, and sometimes to diagnose diabetes. The generally accepted reference range for Hemoglobin A1c (HbA1c) is between 4% and 6%.

Physical Activity Level Change: Assessed via International Physical Activity Questionnaire-short form (IPAQ) to evaluate weekly physical activity levels. The questionnaire provides information about the time spent by the individual in light, moderate, and vigorous activities and sitting in the last 7 days. The MET-min / week score is obtained by multiplying the MET value (metabolic equivalent) by days and minutes for each activity level. Physical activity levels are classified as: Physically inactive (<600 MET-min / week),

Low physical activity (600-3000 MET-min / week), and

Adequate physical activity (> 3000 MET-min / week).

A higher score is associated with a higher physical activity level.

Functional Capacity Change with Timed Up And Go Test: The participant will sit on a chair without armrests, stand up with the command to start, walk 3 meters towards the designated point, turn around and walk to the starting point again and sit. The test is repeated 3 times and the average is taken. The time will be recorded in seconds. As time increases, the risk of falling increases.

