Date: September 1, 2021

Title: Comparison Effects Of Blue Prescription Program, Home Exercise Program And Supervised Exercise Approaches On Type 2 Diabetic Women.

Identifiers: NCT05479435

Statistical Analysis Plan

SPSS 22.0 for MacBook was utilized to analyze the data. The Shapiro-Wilk test was employed to assess whether the data exhibited a normal distribution. Mean, standard deviation, median, and frequency were provided for quantitative data and compared using ANOVA test. Chi-square test was applied for qualitative data analysis. ANCOVA test was utilized for intergroup comparisons of normally distributed data, and Tukey test was used for post hoc analyses. For intra-group comparisons, data were analyzed with paired t-test. Intergroup comparisons of non-normally distributed data were conducted using the Kruskal-Wallis test, and intragroup comparisons were performed with the Wilcoxon signed-rank test. Mann-Whitney U test was employed for pairwise comparisons. The significance level was set at $p \leq 0.05$

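### Do the pairwise Mann-Whitney tests inflate the false-positive rate because the SAP states neither a Kruskal-Wallis gate nor an adjustment?

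*SAP*

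**What the plan says.** The SAP is a single section. For outcomes that pass the normality check, it uses ANCOVA between groups and then states that "Tukey test was used for post hoc analyses". For the others, "Intergroup comparisons of non-normally distributed data were conducted using the Kruskal-Wallis test"; the same sentence gives Wilcoxon signed-rank for changes within a group. The next sentence reads "Mann-Whitney U test was employed for pairwise comparisons". The last sentence sets one level for everything: "The significance level was set at" p ≤ 0.05.

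The section does not make the Mann-Whitney tests conditional on Kruskal-Wallis, and it names no Bonferroni, Holm or other adjustment. The protocol has no statistical text that would settle the matter. Its Experimental Groups section lists three programmes, so each outcome has three pairs. On numbers, its Participants paragraph says only "They were 60 people who were assigned to the groups by using a randomization program".

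**The concern.** Three tests at 0.05 on one outcome give three chances of a false claim. In the normal branch Tukey brings its own protection against this; a plain Mann-Whitney test does not. If an analyst read all three Mann-Whitney results whatever Kruskal-Wallis showed, the protection would depend on which side of the Shapiro-Wilk test an outcome fell. It would also be open to choose between the two readings after seeing the data. Comparing the three programmes is the purpose of the trial, so a false pairwise claim would bear on its main message.

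**Working it through.** **Inputs.** Level 0.05 and the test names: SAP. Three arms, hence three pairs: SAP title and protocol, Experimental Groups. Total of 60: protocol, Participants. Two-sided tests and 20 per arm are assumptions, because the documents state neither sidedness nor allocation ratio. The documents give no familywise error rate or power figure, so there is nothing of the plan's own to reproduce beyond the 0.05 level.

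**Step 1: bounds for three tests with neither gate nor adjustment, no arm different.** The simple upper bound is 3 × 0.05 = 15%. Independent tests would give 1 − (1 − 0.05)³ = 14.3%. The pairs share arms, so the true rate is lower. In large samples it is the upper tail of the studentized range for three groups at 1.96 × √2 = 2.77, which is 12.2%.

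**Step 2: finite samples.** Simulation with no arm different used tie-corrected Kruskal-Wallis (chi-square, 2 df) and two-sided Mann-Whitney by normal approximation. There were 200,000 replicates per setting, and 40,000 for 200 per arm. The table gives the chance of at least one false pairwise claim on one outcome.

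| Group sizes | Neither gated nor adjusted | Gated on Kruskal-Wallis | Bonferroni, ungated |
|---|---|---|---|
| 20/20/20 | 12.1% | 4.8% | 4.2% |
| 17/17/17 | 12.0% | 4.7% | 3.8% |
| 15/20/25 | 12.2% | 4.8% | 4.1% |
| 20/20/20, five-level ordinal | 12.1% | 4.7% | 4.0% |
| 200/200/200 | 12.2% | 5.0% | 4.5% |

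Group sizes and ties hardly matter. The shape of a continuous outcome does not matter at all here, because rank tests are distribution-free when no arm differs.

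**Step 3: is the gate enough?** With three arms there are three cases.

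- All arms equal: Kruskal-Wallis holds the error at about 5%.
- One arm different: one true null pair is left, tested once at 0.05. With 20 per arm and normal data shifted by 0.3 to 3 SD, the error on that pair is 3.1–4.9% gated and 4.8–5.0% ungated.
- All arms different: no true null pair remains.

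The gate therefore suffices, and the 12% arises only when the pairs are neither gated nor adjusted and no arm differs.

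**Step 4: which reading does the text support?** Side by side, the two branches have the same order: ANCOVA then Tukey, Kruskal-Wallis then Mann-Whitney. The comparison between groups is assigned to the three-group test, and the pairwise test comes after it. That is the usual sequence of an overall test and its follow-up.

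**Step 5: what would a change do?** On the follow-up reading, a sentence stating the gate alters no result. Using Holm in place of the gate would lower the power for a given true pair. At an assumed shift of 0.8 SD with 20 per arm, gated against Holm is:

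- Normal data: 60.3% against 51.8%, a loss of 8.5 points.
- Exponential data: 86.7% against 79.8%, a loss of 6.9 points.

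A continuity correction moves the Holm figure by about one point (50.5% in place of 51.8% with normal data). The exponential case is nearer to the outcomes this branch is meant for, though the documents give no distributions.

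**The case for a change.** The strongest case for a change is that the text does not exclude the ungated reading. The Mann-Whitney sentence stands alone and, unlike the Tukey clause, is not labelled as post hoc. The two readings can also disagree. With no arm different, the ungated reading claims a pair and the gated one does not in 12.2% − 4.8% = 7.4% of data sets; with normal data the figure is about 16% at a 0.5 SD shift and 13% at 0.8 SD. A sentence in the SAP would be nearly free. If the ungated reading had been intended, the gate would cost some power: at 0.8 SD about 7 points with normal data (66.9% to 60.3%) and about 2 points with exponential data (88.8% to 86.7%).

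The silence is real and the figures are right. What does not stand is the step from silence to a wrong result. The harm needs three things together: an outcome in the non-normal branch, an analyst who disregards a non-significant Kruskal-Wallis test, and no true difference between arms. The documents do not show how many outcomes meet the first condition, and the second runs against the order in which the SAP sets out its tests. The protocol also lists well over a dozen outcomes without naming a primary one, so a correction within one outcome and one branch would do little for the trial's overall risk of false claims.

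**Conclusion.** No change to the plan follows. The SAP leaves out a detail; it does not state a rule that gives a wrong answer. On the natural reading, with Mann-Whitney following a significant Kruskal-Wallis test, the error rate per outcome is about 5% when no arm differs, and no higher on the remaining pair when one arm does. The figure of about 12% belongs only to three tests that are neither gated nor adjusted, with no arm different. These figures assume two-sided tests and 20 per arm, and they barely move with unequal arms, smaller arms or ties. They concern one outcome at a time and say nothing about multiplicity across outcomes. A reader of the results can check the point by seeing whether the Kruskal-Wallis p-value stands beside any pairwise claim.

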Functional Capacity Change with 6-minute Walking Test: It will be performed in a 30 meter long corridor or in an open area. The participant will be asked to walk without running at the highest speed for 6 minutes. Before and during the march, the participant will be verbally encouraged and motivated. How many meters they walked will be recorded as a result of the test. Six-minute walk test results can be interpreted as follows:

Normal: more than 500 meters

Light restriction: 400 to 500 meters

Moderate restriction: 300 to 400 meters

Severe restriction: between 200 - 300 meters

Serious restriction: less than 200 meters.

Fasting Plasma Glucose: Measures blood glucose levels after fasting for 8-12 hours. Assessed at baseline and 12 weeks. The unit of measurement is mg/dL, the reference range is 70-110 mg/dL.

High Density Lipoprotein (HDL): It takes part in the transport of cholesterol from tissues and vessels to the liver and in the synthesis of vitamin D. The unit of measurement is mg/dL, the reference range is 30-96 mg/dL.

Low Density Lipoprotein (LDL): It provides the transport of cholesterol synthesized in the liver to the tissues and blood vessels. The unit of measurement is mg/dL, the reference range is 0- 130 mg/dL.

Total Cholesterol: Total cholesterol is a value that shows the total amount of cholesterol in the blood. In addition to LDL and HDL, triglyceride levels are also used to calculate total cholesterol. The unit of measurement is mg/dL, the reference range is 70-200 mg/dL.

Triglyceride: It is a storage nutrient molecule formed by the combination of fatty acids and glycerol molecules, which form the structure of fats in foods. The unit of measurement is mg/dL, the reference range is 0-250 mg/dL.

C-reactive Protein: It is a protein produced in the liver. It is a protein that is produced by cells and secreted into the blood when the body reacts to conditions such as infection, tumor, trauma, and undertakes various biochemical tasks. The unit of measurement is mg/dL, the reference range is 0-0.5 mg/dL.

Systolic and Diastolic Blood Pressure: Measured with a sphygmomanometer. Baseline and 12 weeks.

Heart Rate: Measured in beats per minute (bpm). Baseline and 12 weeks.

Body Composition Analysis: Assessed using Bioelectrical Impedance Analysis (BIA) and Skinfold Analysis. Baseline and 12 weeks.

Flexibility Measurements: Evaluated using Fingertip-to-floor Distance Measure and Trunk Lateral Flexion Measure. Baseline and 12 weeks.

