Quality of Life, Depression, and Contentment: Assessed using various scales (DQOL, Beck Depression Scale, DTSQ). Baseline and 12 weeks.

Anthropometric Measurements: Height, weight, neck circumference, waist circumference, hip circumference, and Body Mass Index (BMI). Baseline and 12 weeks.

Experimental Groups:

Blue Prescription Group: Participants receive a personalized exercise program, motivational support, and follow-up by a physiotherapist. Communication is maintained throughout the study.

Video-Based Home Exercise Group: Participants receive exercise videos, perform exercises independently, and are monitored via phone calls. Assessments are conducted at 12 weeks.

Supervised Exercise Group: Participants engage in supervised exercise sessions led by a physiotherapist. Training and assessments are conducted at 12 weeks.

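### No outcome is named primary, and about 25 outcomes are each tested between groups at p ≤ 0.05 with no correction across outcomes, so trial-level type I error is far above 5%

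*SAP*

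**What the plan says.** The protocol's Evaluated Parameters section runs from laboratory values through function, body composition and flexibility to questionnaires and anthropometry. It does not label any item primary, secondary or exploratory. HbA1c comes first ("Glycosylated Hemoglobin Change: Hemoglobin A1c is a blood test used to measure the effectiveness of treatment in diabetes"), but its entry neither ranks it nor gives assessment times. Some entries hold several outcomes: the questionnaire entry names three scales ("Assessed using various scales (DQOL, Beck Depression Scale, DTSQ). Baseline and 12 weeks") and the anthropometry entry six measurements ("Height, weight, neck circumference, waist circumference, hip circumference, and Body Mass Index (BMI). Baseline and 12 weeks").

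The SAP names no outcome. It routes data by type and by the Shapiro-Wilk result: ANCOVA between groups if normal, Kruskal-Wallis if not, chi-square for qualitative data. On multiplicity it offers only that "Tukey test was used for post hoc analyses" in the normal branch. In the other branch, "Mann-Whitney U test was employed for pairwise comparisons", with no adjustment stated and no word on whether these tests follow only a significant Kruskal-Wallis result. One level applies throughout: "The significance level was set at" p ≤ 0.05.

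**The concern.** The trial asks whether three exercise programmes differ, and nothing in these documents says which result answers that. Read as written, a difference at p ≤ 0.05 on any outcome, whether neck circumference, triglyceride or a satisfaction scale, counts as significant. With this many chances, an isolated p-value just under 0.05 is weak evidence. A Bonferroni correction over 25 outcomes would require 0.05/25 = 0.002.

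The stake is that one of several programmes is reported as better on the strength of a chance finding, and that the outcome to emphasise can be picked once the results are known.

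**Working it through.** **Plan's own figure.** The only error rate given is 0.05, and it is per test. There is no sample-size calculation or trial-level rate to reproduce. One test at 0.05 gives 0.05.

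**Count of outcomes** (protocol, Evaluated Parameters), grouped into nine domains for this check:

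| Domain | Outcomes | Number |
|---|---|---|
| Glycaemia | HbA1c, fasting glucose | 2 |
| Physical activity | IPAQ | 1 |
| Function | Timed Up and Go, 6-minute walk | 2 |
| Lipids | HDL, LDL, total cholesterol, triglyceride | 4 |
| Inflammation | CRP | 1 |
| Haemodynamics | systolic BP, diastolic BP, heart rate | 3 |
| Body size and composition | BIA, skinfold, weight, neck, waist, hip, BMI | 7 |
| Flexibility | fingertip-to-floor, trunk lateral flexion | 2 |
| Questionnaires | DQOL, Beck, DTSQ | 3 |
| **Total** | | **25** |

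Height is left out because it does not change. BIA and skinfold count as one variable each, which is a minimum. Within-group and pairwise tests are not counted.

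**Independent outcomes.** P(at least one p ≤ 0.05) = 1 − 0.95^m.

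- m = 25: 1 − 0.95^25 = 0.723
- m = 23: 1 − 0.95^23 = 0.693. This drops BMI and total cholesterol as overlapping; the protocol itself says "In addition to LDL and HDL, triglyceride levels are also used to calculate total cholesterol".
- m = 9: 1 − 0.95^9 = 0.370. This treats each domain as a single test, independent of the others.

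The expected number of false-positive overall tests is 25 × 0.05 = 1.25, whatever the correlation.

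**Correlated outcomes.** The documents give no correlations, so these values are assumed. Each simulation used 10,000 runs with no true differences and 20 per group (60 split equally, also assumed). The common-correlation cases up to 0.8 come from baseline-adjusted ANCOVA with an assumed baseline to 12-week correlation of 0.6. One-way F tests gave the same values to within 0.01, and also gave the 0.9 case. The domain cases are from the ANCOVA simulation.

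| Correlation assumed | P(at least one p ≤ 0.05) |
|---|---|
| None | 0.72 |
| Common 0.3 | 0.62 |
| Common 0.5 | 0.49 |
| Common 0.8 | 0.26 |
| Common 0.9 | 0.18 |
| 0.5 within domain, 0 between | 0.68 |
| 0.5 within, 0.2 between | 0.63 |
| 0.7 within, 0.1 between | 0.60 |
| 0.7 within, 0.2 between | 0.59 |
| 0.9 within, 0 between | 0.52 |

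**Within one outcome.** Tukey with three groups and 57 degrees of freedom amounts to a per-pair threshold of about p = 0.019, so the normal branch is covered inside each outcome. In the non-normal branch (20,000 runs), the chance that any of three unadjusted Mann-Whitney tests is significant is 0.122 if they are always run, and 0.050 if they are run only after a significant Kruskal-Wallis test.

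**Effect of correction.** Testing 25 independent outcomes at 0.002 each gives 1 − 0.998^25 = 0.049.

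**The case against.** Several counterpoints have substance.

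- **A primary may be named elsewhere.** These are short documents carrying a registry identifier, and the registry record was not available. The finding is about these documents. If a primary was fixed beforehand, stating it here with its date settles that part.
- **Routing is inferred.** The SAP names no outcome and no ANCOVA covariate. IPAQ and the 6-minute walk have categories in the protocol and could go to chi-square. That would still be a between-group test at 0.05, so the count stands; baseline adjustment in the simulation is an assumption.
- **The outcomes are correlated, so 72% is too high.** It is the upper end. A common correlation of 0.9 brings the figure to 18%, but that is hard to believe for a list that includes CRP, trunk flexion and depression score.
- **A chance hit is not a false trial conclusion.** True where a primary or a success rule exists. Here neither is stated, so nothing separates the two. Calling the trial exploratory would be legitimate, but neither document does so.
- **The 0.002 cut-off is strict.** It is. Holm's later steps admit some larger p-values, and p = 0.003 is not the same evidence as p = 0.049.
- **A primary named now may be post hoc.** The SAP reports that "SPSS 22.0 for MacBook was utilized to analyze the data", so this is a real limit on the remedy.

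**Conclusion.** The concern holds. In these documents no outcome is primary, about 25 outcomes share one per-test level of 0.05, and nothing corrects across them. Under no true differences, the chance of at least one significant between-group test is 72% with independent outcomes, 59–68% with within-domain correlations of 0.5–0.7 and between-domain correlations of 0–0.2, and 18% at the most extreme correlation tried. Even the last is 0.18/0.05 = 3.6 times nominal.

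The exact figure depends on correlations the documents do not give, and the simulations assume 20 per group. The conclusion that the rate is far above 5% depends on neither. Counting within-group tests and ungated Mann-Whitney tests would add further chances of a false positive.

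**What to change.** 1. **Name one primary endpoint**, for example HbA1c at 12 weeks. Both the choice and the time point are inferences: HbA1c is listed first, and the home and supervised group descriptions place assessments at 12 weeks.
2. **State its test.** Use three-group ANCOVA adjusted for the baseline value at 0.05, with Tukey-adjusted pairs. If the non-normal branch is kept, use Kruskal-Wallis on the 12-week change with Holm-adjusted Mann-Whitney pairs. With only three groups, an explicit rule that the pairs follow only a significant Kruskal-Wallis test would also serve. Committing to one test in advance would avoid a data-dependent choice for the primary.
3. **Treat the other outcomes** as secondary with Holm adjustment across them, or as exploratory with no significance claim. If primary and secondary claims are to share a single 5%, test the secondaries only after a significant primary. Otherwise the two families together can reach 0.05 + 0.05 = 10%.
4. **Disclose timing.** State whether the primary was chosen before outcome data were seen. If it was not, report all outcomes as multiplicity-adjusted or exploratory.

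The cost is protocol and SAP wording plus the disclosure, with no extra participants or procedures. The downside is fewer significant secondary results. With 24 secondaries the first Holm step is 0.05/24 = 0.0021. At 60 participants in three groups and 80% power, the detectable effect then rises from Cohen's f = 0.41 to 0.58, with no covariate gain counted. The primary keeps the full 0.05.
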